The study has a treatment period and a follow-up period. The treatment period has scheduled visits planned depending on the subject's influenza vaccination history and age of the subject and ends 28 days after last vaccination. The follow-up period will conclude with a study completion call.		
Treatment period: After vaccination, all subjects will remain under medical supervision and will be monitored for any immediate postvaccination reactions for at least 30 minutes. Local solicited adverse reactions and systemic solicited adverse events will be collected from 30 minutes after vaccination on a Subject Diary Card, and collection will continue for a total of 7 Days. Three (3) days after vaccination parent(s)/LAR(s) will receive a reminder call to complete the Subject Diary Card. Any unsolicited AE and concomitant medication will be collected until 28 days after each vaccine dose.		
Blood samples for serology will be collected prior to vaccination (Day 1) and 28 days after last vaccination at scheduled clinic visits for immunogenicity evaluation or to evaluate CMI response.		
The collection of body temperature, solicited local adverse reactions, solicited systemic adverse events will continue for a total of 7 days on the Diary Card. Training will be provided for the individual(s) who will perform the measurements of local reactions and		

Name of Sponsor:	Protocol number:	Generic name of study vaccine(s):
Seqirus	V130_10	Cell-Based Quadrivalent Subunit Influenza Virus Vaccine (QIVc) US-licensed Egg-Based Quadrivalent Influenza Vaccine (QIV)
body temperature (often a parent(s)/LAR(s)), and for those who will enter the information into the Subject Diary Card.		
Follow-up period: During the follow-up period, safety data including adverse events (AEs) leading to withdrawal, New Onset of Chronic Diseases (NOCDs), Serious Adverse Events (SAEs), and all medications used related to these events will be captured at 90 days and 180 days after last vaccination.		
Study completion: The study will conclude with a study completion call 180 days after last vaccination.		

Name of Sponsor: Seqirus	Protocol number: V130_10	Generic name of study vaccine(s): Cell-Based Quadrivalent Subunit Influenza Virus Vaccine (QIVc) US-licensed Egg-Based Quadrivalent Influenza Vaccine (QIV)
Study Vaccines:		

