Not previously influenza vaccinated subject: A subject that has not received 2 or more doses of influenza vaccine prior to the current influenza season, or who does not know the influenza vaccination history.

Previously influenza vaccinated subject: A subject with a known history of at least 2 influenza doses prior to the current influenza season.

Qualified healthcare professional: Any licensed health care professional who is permitted by institutional policy to perform clinical interventions and assessments such as physical examinations, is trained on the study procedure(s) and who is identified within the site signature and delegation log.

Seroconversion Rate (SCR) based on the HAI assay: Seroconversion rate (SCR) defined as the percentage of subjects with either a prevaccination hemagglutinin inhibition (HAI) titer $<1:10$ and a postvaccination HAI titer $\geq 1:40$, or a prevaccination HAI titer $\geq 1:10$ and a ≥ 4 -fold increase in post vaccination HAI titer.

Seroconversion rates (SCRs) based on the Microneutralization (MN) Assay: SCR is the percentage of subjects with either a prevaccination MN titer $<1:10$ (LLOQ) and a postvaccination MN titer $\geq 1:40$ (4*LLOQ), or a prevaccination MN titer $\geq 1:10$ (LLOQ) and a ≥ 4 -fold increase in postvaccination MN titer.

Solicited adverse events: Either solicited local adverse reactions or solicited systemic adverse reactions.

Trained healthcare professional: Any health care professional who is permitted by institutional policy, trained to perform delegated tasks, is trained on the study procedure(s) and who is identified within the site signature and delegation log.

Treatment period: Per protocol treatment period begins at the time of vaccination and ends 28 days after last vaccination, which is visit 2 for previously influenza vaccinated subjects and at visit 3 for not-previously influenza vaccinated subjects.

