8.1.2 Secondary Endpoints

8.1.2.1 Secondary Safety Endpoints

The measures for assessing safety and reactogenicity are as follows:

1. Percentage of subjects with solicited AEs within 7 days after each study vaccination
2. Percentage of subjects with any unsolicited AEs from Day 1 to Day 29 (in previously vaccinated subjects) and from Day 1 to Day 57 (in not previously vaccinated subjects)
3. Percentage of subjects with any SAEs, NOCDs, AEs leading to withdrawal during the entire study period (ie, from Day 1 to Day 181 for previously vaccinated subjects or from Day 1 to Day 209 for not previously vaccinated subjects).

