5.1 Time points and Visit Windows

A summary of the assessments required at each study visit is described in [\(Appendix A\)](#).

Day 1 is defined as the day of first dose of the vaccination.

Relative days after Day 1 are calculated as (assessment date – Day 1 date) + 1. Relative days prior to Day 1 are calculated as (assessment date – Day 1 date). The day prior to Day 1 is Day -1

The following visit windows will be used.

Table 5.1-1: Visit windows for previously vaccinated subjects

Statistical Analysis Plan

Sponsor Name: Seqirus
Sponsor Protocol ID: V130_10

Study part	Scheduled visit	Time interval (days)
Screening	Screening Visit	< 10 Days before Day 1
Treatment period	Clinic Visit V1	Day 1
	Reminder Phone V1	Day 3 (-1/+1 Day)
	Clinic Visit V2	Day 28 (+ 7 Days)
Follow-up Period	Safety Phone call V3	Day 90 (+ 7 Days)
	Safety Phone call V4	Day 180 (+ 14 Days)

Table 5.1-2: Visit windows for not previously vaccinated subjects

Study part	Scheduled visit	Time interval (days)
Screening	Screening Visit	< 10 Days before Day 1
Treatment period	Clinic Visit V1	Day 1
	Reminder Phone V1	Day 3 (-1/+1 Day)
	Clinic Visit V2	Day 28 (+ 7 Days)
	Reminder Phone	V2 + 2 Days (-1/+1 Day)
	Clinic Visit V3	V2 + 28 Days (+7 Days)
Follow-up Period	Safety Phone call V4	V2 + 90 Days (+7 Days)
	Safety Phone call V5	V2 + 180 Days (+14 Days)

Visit window deviations will be reviewed prior to unblinding.

5.2 Missing Values – Missing Visit.

Missing, unused and spurious data will be dealt with as such. There is no intention to implement any procedure for replacing missing data.

Titer values recorded as <1:10 (or < lower limit of quantification [LLOQ]) will be summarized as 1:5 (or ½* LLOQ).

No imputation of missing solicited or unsolicited AEs will be used but implausible measurement will be removed as described below. The percentage of subjects with missing solicited AE assessments (e.g. missing Patient Diary) and missing Safety Phone Calls or Safety Assessments will be reported for each time period.

Missing immunogenicity values are considered missing completely at random (MCAR) and therefore will not contain information that impact the result of the analysis (i.e., not informative). Imputation methods will therefore not be used.

The PPS will be used for the primary immunogenicity analysis and a supporting analysis will be performed using the FAS Immunogenicity, as noted in Section 4.4 FAS Immunogenicity.

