grouped by MedDRA preferred terms into frequency tables according to SOC. All reported AEs, as well as AEs judged by the investigator as at least possibly related to study vaccine, will be summarized according to system organ class and preferred term within system organ class. These summaries will be presented by vaccination group and by interval of study observation (Day 1 to Day 29, Day 29 to Day 181 in "previously vaccinated" subjects and Day 1 to Day 57, Day 57 to Day 209 in "not previously vaccinated" subjects). When an AE occurs more than once for a subject, the maximal severity and strongest relationship to the vaccine group will be counted.

Separate summaries will be produced for the following categories:

- SAE
- NOCDs
- Adverse events that are possibly or probably related to vaccine
- SAEs that are possibly or probably related to vaccine
- Adverse event leading to withdrawal or early termination
- Adverse event resulting in death
- Adverse events leading to a medically-attended visit during the treatment period

Data listings of all adverse events will be provided by subject. In addition, adverse events in the categories above will be provided as listed data.

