6.5.4 Subgroup Analysis

The immunogenicity analyses will be performed by stratifying for the following subgroups:

- Subjects with pre-vaccination HAI titer <1:10 and pre-vaccination HAI titer \geq 1:10.
- Subjects with pre-vaccination MN titer <LLOQ and pre-vaccination MN titer \geq LLOQ.
- Subjects with and without recent seasonal influenza vaccine (defined as influenza vaccine within the past 12 months).
- Subjects "previously influenza vaccinated" and "not-previously influenza vaccinated".
- Subjects aged "6 through 23 months" and "24 through 47 months".
- Subjects by gender.
- Subjects by race.
- Subjects by ethnicity.

The safety analyses will be performed by stratifying for the following subgroups:

- Subjects "previously influenza vaccinated" and "not-previously influenza vaccinated".
- Subjects with and without recent seasonal influenza vaccine (defined as influenza vaccine within the past 12 months).
- Subjects aged "6 through 23 months" and "24 through 47 months".
- Subjects by gender.
- Subjects by race.
- Subjects by time interval as below:
 - Day 1 to Day 29, Day 29 to Day 181 in "previously vaccinated" subjects
 - Day 1 to Day 57, Day 57 to Day 209 in "not previously vaccinated" subjects.

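### Unsolicited-AE intervals for two-dose children are written as fixed days counted from dose 1, while the treatment period runs to 28 days after the last dose; adjacent intervals also share a day

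*SAP*

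**What the plan says.** **Interval tables.** SAP 6.5.2.3 summarises unsolicited AEs by "Day 1 to Day 29, Day 29 to Day 181" for previously vaccinated (one-dose) children and by "Day 1 to Day 57, Day 57 to Day 209" for not previously vaccinated (two-dose) children. SAP 6.5.4 repeats both pairs for the safety subgroups, and protocol 8.4.3.1.3 gives the same intervals.

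**Endpoint.** Protocol 8.1.2.1 and SAP 3.2.1 take the secondary unsolicited-AE endpoint in two-dose children "from Day 1 to Day 57 (in not previously vaccinated subjects".

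**Study day.** SAP 5.1 states: "Day 1 is defined as the day of first dose of the vaccination". It adds: "Relative days after Day 1 are calculated as (assessment date – Day 1 date) + 1".

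**Treatment period and collection.** The protocol's List of Definitions says: "Per protocol treatment period begins at the time of vaccination and ends 28 days after last vaccination". The synopsis says: "Any unsolicited AE and concomitant medication will be collected until 28 days after each vaccine dose". SAP 2.2 and 6.6 also tie the end of the treatment period to 28 days after the last dose. Protocol 5.5 places study completion 180 days after the last vaccination.

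**Timing of dose 2.** Protocol Table 1-2 and SAP Appendix A schedule the dose-2 visit at V1 + 28 with a window of 0 to +7 days. SAP Table 5.1-2 labels the same visit Day 28 with +7 days.

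**The concern.** The treatment period moves with the actual date of dose 2. The AE intervals, as written, do not. When dose 2 is given after Day 29, some events within 28 days of that dose have onset after Day 57. They are collected as treatment-period events, but the literal interval rule tabulates them under follow-up. Protocol 7.1.2 reserves that period for serious AEs, new-onset chronic disease and AEs leading to withdrawal. The Day 1 to Day 57 rate would then cover fewer post-dose-2 days in some children than in others, and non-serious events would appear in a table not meant for them.

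SAP 6.5.2.3 also uses two clocks. Its main tables use fixed days, while its summary of medically attended events refers to the treatment period, which is defined from the last dose. For a late dose 2 the two cover different spans.

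Separately, the day that closes one interval opens the next, and no rule says which interval takes an event with onset on that day.

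These tables support the safety description for licensure from 6 months of age. Under protocol 3.1 every eligible child below 12 months is treated as not previously vaccinated, and so is scheduled for two doses.

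**Working it through.** **Inputs.** Study day = date − Day 1 date + 1 (SAP 5.1). Dose 2 at V1 + 28, window 0 to +7 (protocol Table 1-2, SAP Appendix A). Treatment period to 28 days after the last dose (protocol List of Definitions). Completion 180 days after the last dose (protocol 5.5), with a completion-call window of 0 to +14 days (protocol Table 1-2).

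**Step 1: reproduce the plan's cut-points.**
- One dose: 1 + 28 = 29 and 1 + 180 = 181.
- Two doses, with dose 2 on Day 1 + 28 = 29: 29 + 28 = 57 and 29 + 180 = 209.

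All four figures reproduce, but 57 and 209 only for a dose 2 given on exactly Day 29.

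**Step 2: move dose 2 across its window.** Days covered after dose 2 = 57 − dose-2 day. Treatment period ends on dose-2 day + 28. The 180-day point is dose-2 day + 180.

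| Dose-2 day | Days covered by Day 57 | Treatment period ends | 180-day point |
|---|---|---|---|
| 29 | 28 of 28 | Day 57 | Day 209 |
| 30 | 27 of 28 | Day 58 | Day 210 |
| 33 | 24 of 28 | Day 61 | Day 213 |
| 35 | 22 of 28 | Day 63 | Day 215 |
| 36 | 21 of 28 | Day 64 | Day 216 |

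At Day 36 the shortfall is 64 − 57 = 7 days. That is 7/28 = 25% of the post-dose-2 days, or 7/64 = about 11% of the whole dose-anchored interval. Days 58 to 64 fall in the follow-up interval, and Days 210 to 216 fall in neither. If the SAP label of Day 28 with +7 days is taken at face value, the latest in-window dose is Day 35 and the coverage is 22 of 28.

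**Step 3: the far end.** Even with dose 2 on Day 29, the completion call may be as late as Day 209 + 14 = 223. With dose 2 on Day 36 it may be as late as Day 216 + 14 = 230.

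**Step 4: boundary days.** Day 29 lies in both intervals for one-dose children, and Day 57 lies in both for two-dose children. SAP 6.5.2.3 counts repeated events with the same preferred term once per subject, but it does not say which interval takes a boundary-day event.

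**Step 5: one-dose children.** Day 29 is always 28 days after their only dose, so they lose no treatment-period coverage. Only the shared boundary day concerns them.

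**The case against.** The best reply is that Days 29, 57, 181 and 209 are nominal visit labels. Protocol 3.4.2 speaks of the Day 57 clinic visit. Protocol 3.9 speaks of the Day 181 or Day 209 call. Protocol 5.5 equates completion 180 days after the last dose with the Day 209 call, and protocol 7.1.2 equates the end of the treatment period with Day 57. The SAP 5.1 formula refers to assessment dates and does not mention AE onset. Its own visit table labels V1 + 28 as Day 28, where the formula gives Day 29. A strictly literal reading would also put in-window sera drawn on Days 58 to 64 outside Day 29/57, which nobody intends.

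Much of this stands. A reader might infer that the cuts are certainly calendar cut-offs; the documents do not settle that, and a programmer may well use dose-relative cuts. But the only study-day definition in the SAP runs from dose 1, and neither document states how an AE is assigned to an interval. The rule therefore has to be written.

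A second reply is that a fixed Day 57 gives every two-dose child the same length of observation. That would be a defensible choice. It is not the treatment period that the documents define.

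A reader might also infer that a Day 209 cut drops serious-AE follow-up. The documents do not support this. The endpoint covers the entire study period with Day 209 as its label. SAP 6.5.2.3 restates no day limit for its separate summaries of serious AEs, new-onset chronic disease, withdrawals and deaths, and all events are listed by subject.

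**Conclusion.** The point holds as a conflict between the written AE intervals and the documents' own treatment-period definition, together with a missing rule for boundary days. On a literal reading the shortfall runs from 0 days (dose 2 on Day 29) to 7 of 28 days (Day 36), or to 6 of 28 if the latest in-window dose is Day 35.

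The consequence is limited to absolute rates in the interval tables and the Day 1 to Day 57 endpoint in two-dose children, plus one shared boundary day on each schedule. The same windows apply to both arms, so nothing in the documents implies a difference between arms. The days at issue are at most Days 22 to 28 after dose 2, so 7-day solicited data are untouched.

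A reader might assume an even spread of dose 2 over the window and quote a mean loss of 3.5/28 = 12.5%. That should not be used as a loss estimate: the documents give no distribution of dose-2 timing, and a share of post-dose-2 days is not a share of events.

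The conclusion needs only the ordinary window. Protocol 4.3 and 5.2.2 read differently on whether dose 2 is postponed or withheld when a delay criterion is met. Those passages must be reconciled separately. If doses beyond Day 36 do occur, literal coverage falls below 21 days.

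**What to change.** Use one definition in protocol 8.1.2.1 and 8.4.3.1.3 and in SAP 3.2.1, 6.5.2.3 and 6.5.4:

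- **Treatment interval:** first vaccination through 28 days after the last study vaccination received.
- **Follow-up interval:** the next day through the study completion call.
- **Assignment:** each event goes to exactly one interval, by onset date.

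For dose 2 on Day 29 this gives Days 1 to 57 and then Day 58 onward. For dose 2 on Day 36 it gives Days 1 to 64 and then Day 65 onward. For one dose it gives Days 1 to 29 and then Day 30 onward. Days 29, 57, 181 and 209 can remain as visit labels if the text says that they are labels. The SAP should also state that a child scheduled for two doses who receives only one is handled by the same rule, because the treatment interval then ends on Day 29.

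The cost is a wording change in both documents and one derived interval variable. No new data are needed.

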6.5.2.4 Combined Solicited and Unsolicited Adverse Events

A summary of the number of subjects with all combined solicited (regardless of their duration) and unsolicited AEs will be provided, regardless of their duration and recurrence. A further differentiation of combined AEs according to seriousness, severity, or relationship will not be performed. For clinicaltrials.gov and EudraCT posting purposes, a summary of combined solicited and unsolicited non-serious AEs will be produced by System Organ Class and according to occurrence of each event.

6.5.2.5 Body weight and temperature

Body weight and temperature, recorded prior to vaccination, will be provided as a by-subject listing.

6.5.2.6 Physical Examination

Physical Examination Findings will be provided as a by-subject listing.

6.5.3 Analysis of Secondary Immunogenicity Objective(s)

The measures for immunogenicity will be determined by HAI and MN assay for Day 1 and Day 29/57.

Humoral immune response in terms of HAI antibodies against A/H1N1, B/Victoria and B/Yamagata strains, using cell- and egg- derived target virus for both Seqirus QIVc and the QIV comparator.

Statistical Analysis Plan

Sponsor Name: Seqirus
Sponsor Protocol ID: V130_10

- GMTs: Geometric mean of HAI titers pre-vaccination (Day 1) and post-vaccination (Day 29/57);
- Geometric mean ratio (GMR), defined as the fold increase in serum HAI GMTs post vaccination (Day 29/57) compared to prevaccination (Day 1). Geometric Mean Ratio from Day 1 to Day 29 or Day 57.
- Seropositivity rates (percentages of subjects with HAI titer $\geq 1:10$) at Days 1 and 29/57.
- Percentage of subjects with HAI titer $\geq 1:40$ at Days 1 and 29/57.
- SCR by HAI assay.

Neutralizing antibody titers against A/H3N2 vaccine strains, using cell- and egg-derived target virus:

- GMT by MN assay at Days 1 and 29/57
- GMR, defined as the fold increase in serum MN GMT post vaccination (Day 29/57) compared to prevaccination (Day 1)
- Seropositivity rates (percentages of subjects with MN titer $\geq 1:10$ (LLOQ)) at Days 1 and 29/57
- SCR by MN assay

Neutralizing antibody titers against A/H1N1, B/Victoria and B/Yamagata vaccine strains, in a subset of subjects:

- GMT by MN assay at Days 1 and 29/57
- GMR, defined as the fold increase in serum MN GMT post vaccination (Day 29/57) compared to prevaccination (Day 1)
- Seropositivity rates (percentages of subjects with MN titer $\geq 1:10$ (LLOQ)) at Days 1 and 29/57
- SCR by MN assay

6.5.3.1 Statistical Hypothesis

No statistical testing will be performed for the secondary immunogenicity objectives.

6.5.3.2 Statistical Methods

All statistical analyses for HAI (or MN) titers will be performed on the logarithmically transformed (base 10) values. Individual HAI titers below the detection limit (<10) will be set to half of that limit (5). Individual MN titers below the lower limit of quantification (LLOQ), will be set to half of that limit.

Unadjusted for GMT, GMRs and pertaining two-sided 95% CIs will be calculated assuming log-normal distribution of the titers and will be completed by providing minimum, maximum and median titers for each vaccine group.

Binary data (i.e. percentages of subjects with seroconversion and with titer $\geq 1:40$) will be summarized for each group using crude estimates and will be reported together with 2- sided exact 95% CIs. No multiplicity adjustment to the CI levels will be implemented.

For immunogenicity data, it may be reasonable to consider missing immunogenicity values MCAR, i.e. not informative. Therefore, the key secondary analysis will

comprise a complete case analysis only, without introducing any bias. Imputation methods will not be used.

6.5.4 Subgroup Analysis

The immunogenicity analyses will be performed by stratifying for the following subgroups:

- Subjects with pre-vaccination HAI titer <1:10 and pre-vaccination HAI titer \geq 1:10.
- Subjects with pre-vaccination MN titer <LLOQ and pre-vaccination MN titer \geq LLOQ.
- Subjects with and without recent seasonal influenza vaccine (defined as influenza vaccine within the past 12 months).
- Subjects "previously influenza vaccinated" and "not-previously influenza vaccinated".
- Subjects aged "6 through 23 months" and "24 through 47 months".
- Subjects by gender.
- Subjects by race.
- Subjects by ethnicity.

The safety analyses will be performed by stratifying for the following subgroups:

- Subjects "previously influenza vaccinated" and "not-previously influenza vaccinated".
- Subjects with and without recent seasonal influenza vaccine (defined as influenza vaccine within the past 12 months).
- Subjects aged "6 through 23 months" and "24 through 47 months".
- Subjects by gender.
- Subjects by race.
- Subjects by time interval as below:
 - Day 1 to Day 29, Day 29 to Day 181 in "previously vaccinated" subjects
 - Day 1 to Day 57, Day 57 to Day 209 in "not previously vaccinated" subjects.

6.5.5 Analysis of Exploratory Immunogenicity Objectives

Exploratory immunogenicity endpoints of homologous CMI responses will be summarized using descriptive statistics by treatment group at baseline (Day 1), and Day 29/57 in a subset of 84 subjects.

For each vaccine antigen analyzed and each pattern including single response variables, separated by vaccine group and visit, the mean percentage, the 2-sided 95% confidence interval, standard deviation, median, minimum, and maximum were calculated to characterize the vaccination groups. Between-group differences incl. 2-sided 95% CI and within-group differences (relative to baseline) incl. 2-sided 95% CI were calculated using ANCOVA with vaccine group as qualitative factor adjusted for baseline values. All available data were included in the analysis irrespective of any protocol deviation

In case of additional exploratory immunogenicity analyses, the immune response will be further characterized similar to the analysis of secondary immunogenicity endpoints.

